Project Design	Longitudinal cohort study in which participants will receive either 8 weeks of statin therapy and a seasonal quadrivalent influenza vaccine (QIV) or a seasonal quadrivalent influenza vaccine (QIV) alone. Immune responses in the blood will be assessed.
Primary Objective	Compare the antibody (Ab) response to QIV in statin recipients and non-recipients.
Secondary Objectives	Assess the safety profile of statin therapy + QIV v/s QIV alone.
Exploratory Objectives	
 Explore the effect of statin therapy on immune signatures after vaccination. Evaluate the effect of statin therapy on plasma cytokine responses to vaccination.
Research Intervention(s)/Interactions	Initiation of 8 weeks of statin therapy and immunization with a single dose of seasonal QIV.
Study Population	Healthy adults (age 18 to 50 years) without history of statin use and without current receipt of seasonal influenza vaccine or recent influenza infection.
Sample Size	N=30 in the Statin + QIV arm. N=30 in the QIV alone arm.
Study Duration for individual participants	8 months.
Study Specific Abbreviations/ Definitions	Ab –antibody QIV – seasonal quadrivalent influenza vaccine
Funding Source	Hope Clinic Internal funds

2. Objectives

Primary Objective:

Compare the antibody (Ab) response to QIV in statin recipients and non-recipients.

Secondary Objective:

Assess the safety profile of statin therapy + QIV v/s QIV alone.

Exploratory Objectives:

1. Explore the effect of statin therapy on innate immune signatures to QIV.
2. Evaluate the effect of statin therapy on plasma cytokine response to QIV.

3. Background

Statins are widely used for their lipid-lowering and cardiovascular protective effects¹. Additional research has shown that statins can be anti-inflammatory, and play a part in modulating the immune system²⁻⁴. These effects are called into action in events such as pneumonia⁵, influenza^{6,7}, and sepsis⁸.

Statins decrease cholesterol synthesis by inhibiting the enzyme HMG-CoA reductase. This results in the activation of the SREBP pathway which promotes cholesterol uptake and synthesis⁹. One study investigated the role of SREBP signaling in B cell responses using a mouse model. It was demonstrated that SREBP inhibition decreased gene activation involved in lipid metabolism and fatty acid synthesis which is essential for antibody production. This resulted in a decrease in B cell differentiation to plasma cells and a deficiency in production of high-affinity antibodies¹⁰.

Studies evaluating the effects of statins on the immune system's response to the influenza vaccine have provided mixed results. Many studies have shown that chronic statin therapy negatively influences the influenza vaccine's efficacy, with titer levels markedly lower than in statin nonusers¹¹. Other researchers showed that statin therapy may only partly alter the immune response to the influenza vaccine against some strains, while the protection against other strains remained intact¹². Another study involving a large population of statin users and statin nonusers, found that statin users had lower influenza vaccine effectiveness against acute respiratory illness than nonusers¹³. However, other retrospective cohort studies found that the difference in vaccine effectiveness between statin users and nonusers was not significant and did not translate into a difference in the clinical course of the disease^{14,15}.

One study compared the gut microbiota in statin users and statin non users. The results proved that statin therapy significantly lowered the prevalence of gut microbiota dysbiosis. The reshaping of the microbiota to limit potentially harmful bacteria and increase beneficial bacteria, as well as the increase in gut microbiota diversity may contribute to a better vaccine response¹⁶. In fact, Oh et al. conducted a study on influenza vaccine which showcased the role of the microbiota in boosting vaccine immunity. The findings prove that the microbiome is one of the factors contributing to the effectiveness of vaccines¹⁷.

Systems vaccinology involves applying systems biology principles to the field of vaccinology with a view to predict vaccine efficacy. Our objective is to identify molecular signatures or patterns of gene expression that are altered after the use of chronic statin therapy and analyze the innate and adaptive immune mechanisms responsible for this effect¹⁸.

4. Study Endpoints

Primary Endpoint:

Magnitude of antibody responses to QIV at 29 days after vaccination in each study group.

Secondary Endpoint:

Frequency and severity of adverse events until Day 29 and serious adverse events until D181 after vaccination in each study group.

Exploratory Endpoints:

1. Identification of innate immune signatures until 7 days after vaccination that predict the magnitude and durability of Ab response Days 29, 91 and 181 after vaccination in each study group.
2. Plasma cytokine response until 7 days after vaccination in each study group.

5. Study Intervention/Investigational Agent

5.1 Description

Atorvastatin therapy

Atorvastatin is a lipid-lowering agent of the statin family that functions by blocking a rate-limiting enzyme, HMG-CoA reductase, in the lipid metabolism. This agent is commonly used for primary and secondary prevention of dyslipidemia. Participants will be asked to take Atorvastatin 80 mg daily at night, for 4 weeks prior to the vaccination and continue the statin therapy for 4 weeks after vaccination.

The 80mg dose of atorvastatin allows for evaluation of the immunologic effects of statin medication with a short duration of therapy prior to vaccination. Studies have shown that 80mg of atorvastatin for 1 month affects inflammatory responses while lower doses of statin for longer periods may not. The 80mg dose reduced inflammation related to including NF- κ B while other studies looking at lower doses of statin for 3 months did not find a difference in NF- κ B¹⁹. Observational studies have investigated the dose-response question for statin therapy and vaccine effect but they either had insufficient sample size for that question²⁰ or there was a trend toward lower vaccine efficacy with higher dose statin, though this was not statistically significant²¹.

Quadrivalent seasonal influenza vaccine

The FDA-approved quadrivalent seasonal influenza vaccine contains four distinct strains: two influenza A viruses and two influenza B viruses. The approved seasonal QIV will be purchased from the manufacturer to be given for each season of influenza.

5.2 Drug Handling

Atorvastatin and QIV will be stored at the Emory Investigational Drug Service (IDS) per the manufacturer's instructions. It will be prepared by an IDS pharmacist on site at the Hope Clinic satellite IDS. Logs of receipt, temperature, maintenance, and disposal will be maintained in the study file.

The Atorvastatin therapy will be dispensed by a study coordinator, nurse or provider at the Hope Clinic with clear instructions on how and when to take the pills. Participants will be instructed to contact the clinic staff immediately if they develop concerning symptoms following the administration of the drug.

QIV will be administered by a study nurse or provider at the Hope Clinic as a single 0.5mL intramuscular injection in the deltoid muscle.

5.3 Accountability Procedures for Study Products

The IDS pharmacist will maintain accurate drug accountability logs which will be kept at the IDS pharmacy until the completion of the study. Upon completion of the study, a final drug accountability will be done. Following the completion of the drug accountability, the original copies of the logs will be maintained. When the vaccine is administered to a participant, the date, time and location of the injection will be recorded in the participant's study source documentation records.

6. Procedures Involved

For a schedule of procedures, see Appendix A.

6.1 Screening and Consenting (D-60 to D-32)

6.1.1 Potential participants interested in the study will respond to study ads. Recruiters from the Hope Clinic will then contact them for a telephone screening, during which the research study will be explained in lay terms and eligibility criteria will be reviewed. If all eligibility criteria are met and the participant remains interested, an in-person screening appointment will be scheduled. Prior participants in other studies conducted at the Hope Clinic, and who had indicated their willingness to participate in other studies may also be contacted for a telephone screening visit.

6.1.2 At the in-person screening appointment , study staff will review the informed consent form with the participant and will answer all questions related to the study. Once the participant signs the informed consent, they will be assigned a unique study participation number. The following procedures will be performed:

- Recording of demographic information and review of medical history including recent influenza infection, including current medication use (medications that may interact with Atorvastatin) and vaccination history (previous receipt of influenza vaccines).
- Vital signs and targeted physical exam as indicated based on review of participant health status.
- A urine pregnancy test will be performed if the participant is a woman of child-bearing potential.
- Blood sample collection for baseline immunological assays and baseline clinical labs. Clinical labs may be repeated at investigator discretion.

6.1.3 Participants who remain eligible for the study will be randomized to either Statin therapy + QIV arm or QIV alone arm. Participants randomized to the Statin therapy+ QIV arm will receive the Atorvastatin pills with clear instructions on how to use them in a separate visit.

6.1.4 Clinical staff wil provide participants with a stool collection kit along with an information sheet explaining how the stool collection is done. The steps will be explained to the participant who will be asked to provide a stool sample on D-31, D1, and D29.

6.2 Initiation of Statin therapy (D-31 to D-29)

Participants randomized to the Statin + QIV arm will be asked to come back to the Hope Clinic for an extra visit one month prior to date of vaccination. The following procedures will be performed:

- Review of interim medical history for any updates or changes.
- Review of concomitant medications for any updates or changes.
- Recording of vital signs and targeted physical exam if indicated.
- Blood sample collection.
- Stool sample collection.
- Re-verification of eligibility criteria.
- Completion of prescription form by licenced provider and dispension of Atorvastatin 80mg by the pharmacy at the clinic.
- Distribution of the drug to participant by study coordinator or nurse or provider with clear instructions on modalities of administration of the drug and common side-effects.

6.3 Phone call (15 days after initiation of Statin therapy)

Fifteen days after initiation of Atorvastatin therapy, the study staff will call participant to assess participant compliance and any complications due to the drug. If needed, the participant will be asked to come to clinic for further assessment. The call will last approximately 15 minutes.

6.4 Vaccination Visit (D1)

The following actions will be performed on the day of vaccination:

- Review of inclusion and exclusion criteria to confirm eligibility.
- Review of medical history, concomitant medications and vaccinations.
- Collection of vital signs.
- Completion of a targeted physical exam if needed.
- For participants of child-bearing potential, a negative urine pregnancy test is required.
- For the statin therapy group, participant compliance to the drug will be assessed.
- Blood samples for immunologic assays will be collected prior to vaccination
- Stool sample collection
- Participants will receive the CDC influenza vaccine information sheet and review it prior to vaccination.
- Participants will then receive QIV via the intramuscular route, administered by a clinical research nurse or provider.
- Participants will be observed for a minimum of 15 minutes for any immediate hypersensitivity reactions.
- Participants will be asked to fill a memory aid for 7 days after vaccination. Participants will have the option of an online survey or paper memory aid.

The visit will last approximately 60 minutes.

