6.5 Follow-up Visits (D2, D4, D8, D15, D29, D91, D181)

All participants will return for follow-up visits following vaccination. During these visits, study personnel will:

- Review the participant's current health status.
- Note any changes in health history since the screening visit, including current medication use and vaccination history.
- Collect blood samples for immunological assays.
- Review memory aid until Day 8.
- Record adverse events until Day 29.
- Record serious adverse events until D181.

The visit will last approximately 30 minutes.

Participants will be asked to provide a stool sample on D29 in addition to the above described procedures.

7. Statistical Analysis Plan

This is an exploratory, non-placebo controlled analysis of immune responses obtained from blood samples. This will provide us with descriptive data to analyze immune responses.

Analysis of Primary Endpoint: Magnitude of antibody responses to QIV at 29 days after vaccination in each study group.

Analysis of Secondary Endpoint: Frequency and severity of adverse events until Day 29 and serious adverse events until D181 after vaccination in each study group.

Descriptive analysis, e.g. tables and histograms, will be conducted to present severity of all AEs. The frequency will be tabulated. Ad hoc analyses of correlations of reactogenicity events with innate and adaptive immune responses may be conducted.

The study staff will aim to enroll 30 participants in each of the statin therapy+QIV and QIV alone arms.

8. Data and/or Specimen Banking

Participants will be asked for permission for the principal investigator to keep any remaining (residual) specimens derived from venous blood collection for possible use in future research studies, such as examining additional immunological assessments or testing for antibodies against other viruses or bacteria. Future use samples/specimens will not be sold or used directly for production of any commercial product. These samples/specimens are protocol-required; thus, participants must agree to future use of these samples/specimens as a condition of their study participation.

These samples/specimens will be stored at the Hope Clinic and shipped regularly to [REDACTED] lab at Stanford and other collaborating labs. The de-identified (all personal identifying information of the participant will be removed) samples/specimens will be labeled and stored in freezers at -80°C or in liquid nitrogen tanks.

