18.1 Risks of Investigational Products/Interventions

Atorvastatin therapy

Atorvastatin is an FDA-approved lipid lowering drug that is widely used. In some cases, this statin may be associated with the following risks:

- Diarrhea, nasopharyngitis, arthralgia in 4-14%

- Insomnia in 3%
- Nausea and dyspepsia in 4-6%
- Increased transaminases in 2-3%
- Muscle spasms, myalgia, musculoskeletal pain in 3 to 8%

Treatment with Atorvastatin may also be rarely linked to more serious risks such as:

- Hypersensitivity or severe allergic reaction including anaphylaxis, angioneurotic edema, erythema multiforme, Stevens-Johnson syndrome, and toxic epidermal necrolysis
- Acute liver failure or decompensated cirrhosis
- Nonserious and reversible cognitive side effects
- Fatal and nonfatal hepatic failure
- Increases in HbA1c and fasting serum glucose levels
- Myopathy and rhabdomyolysis: risk increased with renal impairment, age>65 and hypothyroidism
- Increases in serum transaminases. These changes occurred following the start of statin therapy, were not accompanied by other symptoms, and reversible after drug discontinuation
- Persistent increases to more than three times the ULN in serum transaminases have occurred in approximately 0.7% of patients
- Immune-mediated necrotizing myopathy: characterized by muscle biopsy showing necrotizing myopathy without significant inflammation, improvement with immunosuppressive agents, proximal muscle weakness, and elevated serum creatine kinase, which persist despite discontinuation of statin treatment

A scientific statement from the American Heart Association²² supports the safety of statin therapy including in people at low risk for cardiovascular disease, noting the risk of statin-induced serious muscle injury is <0.1% and risk of serious hepatotoxicity is <0.01%. Current product labels do not include the need for routine monitoring of liver enzymes if these are normal prior to initiating statin therapy. For safety, liver enzymes and creatine phosphokinase (CPK) will be monitored on a regular basis during the study.

Seasonal influenza vaccine

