The potential harms of receiving the influenza vaccine include, but are not limited to: pain and redness at the injection site, muscle aches, fatigue, and headache. These reactions occur in 10-25% of adults who receive influenza vaccine. Serious adverse reactions including anaphylaxis and Guillain-Barré syndrome are possible, but rare. Potential participants with a history of severe allergic reaction to any component of the vaccine or Guillain-Barré syndrome after previous influenza vaccination will not be enrolled. For further details, see the attached package insert.

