22.2.7 Collecting and Recording Adverse Events and Pregnancy

Adverse events may be identified during this study through any of these methods:

- Examination of the participant during study visits.
- Questioning the participant during study visits.
- Receiving a safety contact from the participant at any time during the study

Note: participants will be asked to call the site if they develop any of the following:

- Any adverse event that limits self-care activities of daily living (e.g. bathing, dressing and undressing, feeding self, using the toilet, taking medications, and not bed ridden) even if he/she decides not to seek medical care

Reactogenicity of any grade is collected for 7 days after vaccination.

Serious adverse events will be recorded if they occur at any time during the study.

A complete recording of safety events in the CRF will include event term; date(s) of onset and resolution/stabilization; assessment of severity; relationship to procedures/intervention(s); expectedness; determination of whether the AE qualifies as serious or non-serious; treatment required; action taken with study participation; and outcome. AEs qualifying as serious also require a narrative of the event. Updates in safety events will be recorded as additional information becomes available.

Information on pregnancies will be collected from the time a participant signs the consent until the participant completes study participation. If a participant becomes pregnant after study entry, the investigator will discuss with the participant and/or the treating provider the known possible risks to the fetus. Participants becoming pregnant after study entry will be withdrawn from the study and followed until the end of the pregnancy for safety. A pregnancy resulting in congenital anomaly/birth defect will be considered a SAE. Any premature termination of the pregnancy will also be reported and assessed as an SAE as needed.

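### The 7-day memory aid has no described pre-dose entry and no new-or-worsened rule, so symptoms already present on D1 after four weeks of atorvastatin may be read as vaccine reactogenicity

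*Combined protocol and SAP*

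**What the plan says.** - **Memory aid.** Section 6.4 lists it last among the D1 steps, after the injection and the observation period: "Participants will be asked to fill a memory aid for 7 days after vaccination". No pre-dose entry is described.
- **What is collected.** Section 22.2.7: "Reactogenicity of any grade is collected for 7 days after vaccination". No condition relates a symptom to its state before the injection, and Section 7 adds none.
- **Statin exposure.** Section 5.1 has the statin arm take atorvastatin "for 4 weeks prior to the vaccination and continue the statin therapy for 4 weeks after vaccination". The QIV-alone arm has no such exposure.
- **Overlapping symptoms.** For atorvastatin, Section 18.1 lists "Muscle spasms, myalgia, musculoskeletal pain in 3 to 8" per cent and "Nausea and dyspepsia in 4-6" per cent. For the vaccine, it lists "muscle aches, fatigue, and headache. These reactions occur in 10-25% of adults who receive influenza vaccine". Section 22.2.3 adds nausea as a possible systemic vaccine reaction, without a rate.
- **Other safety recording.** Appendix A marks adverse events at V2, at the phone call 15 days into statin therapy, and at V3 (D1). Under Section 22.2.7 each record holds onset date and severity. Section 22.3.2 makes a single related/unrelated call to study participation.
- **Use of the data.** Section 7 tabulates adverse events descriptively and adds: "Ad hoc analyses of correlations of reactogenicity events with innate and adaptive immune responses may be conducted".

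**The concern.** A participant with statin myalgia or nausea on the morning of D1, still present that evening, can enter it on the memory aid as a symptom within the 7-day window. Nothing in the plan tells the analyst to set it aside. Atorvastatin is given in one arm only, so the drug-caused part of this carry-over raises apparent reactogenicity in the statin arm alone.

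Two readings are at stake. One is vaccine-specific: whether vaccinees on a statin react more or less to QIV. The other is the possible correlation of reactogenicity with innate and adaptive responses, where a statin symptom mislabelled as a vaccine reaction adds error that differs by arm. With 30 participants per arm and a 10-25% reaction rate, only 3 to 7.5 participants per arm are expected to have the event (30 × 0.10 = 3; 30 × 0.25 = 7.5), so one or two misclassified participants matter.

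**Working it through.** The plan gives no figure for reactogenicity, so there is none to reproduce. The check sizes the possible carry-over from the plan's own rates.

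**Inputs.** n = 30 per arm (synopsis). Vaccine rate v = 0.10 to 0.25, statin muscle rate s = 0.03 to 0.08, statin nausea/dyspepsia rate s = 0.04 to 0.06 (all Section 18.1).

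**Assumptions.** Every listed statin symptom is caused by the drug, present on D1 and still present afterwards; none is removed under Section 17; statin and vaccine symptoms are independent.

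**Formula.** Apparent statin-arm rate = v + (1 − v)s, so excess = (1 − v)s.

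| Symptom | v | s | Apparent rate | Excess (points) | Extra of 30 |
|---|---|---|---|---|---|
| Muscle | 10% | 3% | 12.7% | 2.7 | 0.81 |
| Muscle | 10% | 8% | 17.2% | 7.2 | 2.16 |
| Muscle | 25% | 3% | 27.25% | 2.25 | 0.68 |
| Muscle | 25% | 8% | 31.0% | 6.0 | 1.80 |
| Nausea/dyspepsia | 10% | 4% | 13.6% | 3.6 | 1.08 |
| Nausea/dyspepsia | 10% | 6% | 15.4% | 5.4 | 1.62 |
| Nausea/dyspepsia | 25% | 4% | 28.0% | 3.0 | 0.90 |
| Nausea/dyspepsia | 25% | 6% | 29.5% | 4.5 | 1.35 |

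Nausea/dyspepsia is a separate symptom line and is not added to the muscle figure.

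**Sensitivity to v.** The 10-25% covers a group of reactions, not muscle aches alone, and nausea is not in that group, so using it for nausea is an assumption. Whatever v is, the excess cannot exceed s: 8 points (2.4 of 30) for muscle and 6 points (1.8 of 30) for nausea/dyspepsia.

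**Chance of at least one carrier among 30.** This is 1 − (1 − s)^30. Muscle: 1 − 0.97^30 = 60% to 1 − 0.92^30 = 92%. Nausea/dyspepsia: 1 − 0.96^30 = 71% to 1 − 0.94^30 = 84%.

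**Visibility afterwards.** At 30 per arm, and assuming a two-sided 5% test (the plan states none), power to detect the muscle excess is about 4% to 12%. The tabulated rates could neither show it nor exclude it.

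**Could a baseline be rebuilt from the adverse-event record?** Sections 6.2 and 6.3 describe V2 and the call for the statin arm only. The payments in Section 20 agree. Without them, a participant has screening, D1 and seven follow-up visits: 75 + 125 + 7 × 75 = $725, the lower total. Adding the statin visit and one call gives 725 + 100 + 20 = $845, the upper total. QIV-alone participants thus have no scheduled adverse-event contact between screening and D1. On D1, Appendix A marks adverse events for everyone, but Section 6.4 lists a history review without grading of memory-aid items. A rebuilt baseline would not be like-for-like.

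**The case against.** The strongest reply is that pre-vaccination symptoms are recorded. Adverse events are scheduled at V2, the call and D1, with onset date and severity. Section 22.3.1 grades every event, and Section 17 extends its grade-based rules to diarrhea, myalgias and other statin symptoms, which requires them to be graded. That stands: a reader might infer that no pre-vaccination grade exists, and the documents do not support this. The gap is that nothing links that record to the memory aid, its capture is unequal between arms, and the related/unrelated call does not separate statin from vaccine.

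A reader might also infer that pre-existing symptoms are definitely scored as vaccine reactions. No section says so, and the memory-aid form is not reproduced; they may be. Nor is miscounting confined to one arm: background aches or nausea can carry over in either arm, and only the statin-caused part is one-sided.

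The size is also a generous one. Section 18.1 gives no time frame, duration or comparator rate for the statin symptoms. Some may start after D1, resolve before it, or be background that cancels between arms. The Section 17 rules should leave mostly grade 1 symptoms at vaccination, although collection at any grade would still pick those up.

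Finally, the secondary objective compares regimens, descriptively, and statin symptoms belong in that comparison. This stands too. The immune correlations are optional, in a study that calls itself exploratory.

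**Conclusion.** The point holds in a limited form. The plan describes no pre-dose memory-aid entry and no rule confining reactogenicity to new or worsened symptoms, so statin symptoms present on D1 may be read as vaccine reactions. Under the stated assumptions the muscle-symptom excess is about 2 to 7 percentage points (0.7 to 2.2 of 30 participants, or 8% to 42% of the statin-arm count: 2.25/27.25 to 7.2/17.2). The nausea/dyspepsia line is about 3 to 5 points. Both are upper bounds given the 10-25% vaccine rate, because they take every listed statin symptom as drug-caused and present on D1.

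A reader might go further and conclude that the between-arm safety comparison is invalid. It is not: total adverse events by arm remain a sound descriptive comparison of statin plus QIV with QIV alone. What is weakened is any vaccine-specific reading of the 7-day data and the ad hoc correlations with immune responses. This is a cheap improvement to data collection, not a flaw in the primary endpoint or the sample size.

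**What to change.** 1. **Section 6.4 and the memory aid (paper and online).** Add a pre-dose column, completed in clinic on D1 before the injection by both arms, with the same items and grades as the daily entries.
2. **Section 7.** Add a rule such as: *A solicited reaction is a memory-aid symptom that is absent before the injection and appears in the 7 days after it, or that reaches a higher grade than its pre-dose grade. Pre-dose prevalence is reported by arm.* Use the same definition in any correlation with immune responses.
3. **Leave the all-adverse-event table unchanged**, since it serves the regimen comparison.
4. **State the limitation.** Atorvastatin continues after vaccination, so statin symptoms that first appear or worsen on D1-D8 still cannot be separated from vaccine reactions.

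Under the assumptions used above, carry-over at an unchanged grade is no longer counted, so that excess falls to zero. There is a small opposite risk: a vaccine reaction of no higher grade than an existing symptom is missed. At most this affects v × s of participants, from 0.10 × 0.03 = 0.3% to 0.25 × 0.08 = 2.0%, or 0.09 to 0.6 of 30. The pre-dose line by arm lets a reader judge it.

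The cost is one form column, about two minutes at D1 and a short addition to Section 7. Visits, sample size and clinical management do not change. The pre-dose grade cannot be recovered reliably later, so the column must be in place before a participant is vaccinated.
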